As the transmission of HIV and other blood-borne pathogens can occur through contact with contaminated needles, blood, and blood products, appropriate blood and secretion precautions will be employed by all personnel in the drawing of blood and shipping and handling of all specimens for this study, as currently recommended by the Centers for Disease Control and Prevention and the National Institutes of Health.

All infectious specimens will be packaged and sent in accordance with requirements mandated by the International Air Transport Association Dangerous Goods Regulations- Packing Instruction 602.

DATA SAFETY AND MONITORING PLAN

This is a pilot study that will serve to collect preliminary data on the anti-inflammatory effects of zinc in HIV. However, an independent data and safety monitoring board will be established to include an independent HIV expert, a statistician, and a community advocate. The DSMB will meet every 6 months (or earlier as needed) to review safety data and adverse events. The DSMB will function to: review and approve plans for data and safety monitoring for this trial; to review data on a timely basis and to ensure proper conduct and progress of study; to review credentials of investigator and project staff; to make recommendations to project investigator and staff regarding issues of concern; to address adverse events. The DSMB will meet twice a year in Cleveland, Ohio or by phone conferences to review study protocols progress, and safety data. Meetings will be held in an open format, except if privileged data are discussed. At the time of the continuing review, the DSMB report will be prepared by [name] and her staff and will include enrollment and dropout rates, protocol deviations, subjects symptoms, review of clinical and laboratory results.

The DSMB will review interim data to detect evidence of adverse events to determine if the trial should continue as originally designed, should be changed or even stopped based on the data. The DSMB will evaluate the progress of the trial, including periodic assessments of the recruitment goals, protocol adherence, accrual and retention of participants. The DSMB will protect confidentiality of the study subjects.

The Principal Investigator will report all > Grade 2 adverse effects deemed to be possibly, probably or definitely related to study participation to the University Hospitals Cleveland Medical Center CWRU IRB within one week in writing. All >1 Grade 1 adverse effects deemed to be possibly, probably or definitely related to study participation will be collected. The Principal Investigator, investigators, and study nurse will prepare every year an update to renew the University Hospitals Cleveland Medical Center CWRU IRB approval of the clinical studies. In this renewal, investigators will inform the IRB about adverse effects Grade > 1 noted during the performance of the study. Accrual, retention, and data quality and timeliness will be monitored by the Principal Investigator.

Protocol Deviations: All deviations will be documented in the source document and the IRB will review all protocol deviations. Any deviation that may affect study conduct or safety will promptly be reported within 72 hours.

Quality Control Committee: Not applicable

Adverse Events

Definitions

The definitions of Adverse Events (AEs) and Serious Adverse Events (SAEs) are given below. It is of the utmost importance that all staff involved in the study be familiar with the content of this section. The principal investigator is responsible for ensuring this.

Adverse Event

An Adverse Event (AE) is the development of an undesirable medical condition or the deterioration of a pre-existing medical condition following or during exposure to a pharmaceutical product, whether or not considered causally related to the product. An undesirable medical condition can be symptoms (eg, nausea, chest pain), signs (eg, tachycardia, enlarged liver) or the abnormal results of an investigation (eg, laboratory findings, ECG). In clinical studies, an AE can include an undesirable medical condition occurring at any time, including run-in or washout periods, even if no study treatment has been administered.

Any detrimental change in a patient's condition subsequent to them entering the study and during the follow-up period should be considered an AE. When there is a deterioration in the condition for which the study treatment is being used, there may be uncertainty as to whether this is lack of efficacy or an AE. In such cases, unless the reporting physician considers that study treatment contributed to the deterioration or local regulations state to the contrary, the deterioration should be considered a lack of efficacy. Signs and symptoms of disease progression are therefore not considered AEs.

Serious Adverse Event

- A Serious Adverse Event (SAE) is an AE occurring during any study phase (eg, run-in, treatment, washout, follow-up), and at any dose of the investigational product, comparator or placebo, that fulfills one or more of the following criteria:
 - Results in death
 - Is immediately life-threatening
 - Requires inpatient hospitalization or prolongation of existing hospitalization
 - Results in persistent or significant disability or incapacity
 - Is a congenital abnormality or birth defect
 - Is an important medical event that may jeopardize the patient or may require medical intervention to prevent one of the outcomes listed above.

Any event or hospitalization that is unequivocally due to progression of disease, as determined by the investigator, must not be reported as an SAE.

The causality of SAEs (their relationship to all study treatment) will be assessed by the investigator(s)

Reporting of Adverse Events

When recording/reporting AEs, the use of diagnoses is preferred (when possible) to recording/reporting a list of signs and symptoms. However, if a diagnosis is known and there are other signs or symptoms that are not generally part of the diagnosis, the diagnosis and each sign or symptom will be recorded/reported separately.

Illiterate Subjects

Subjects with all levels of literacy will be eligible for this study. The consent document will be read to those volunteers with less than an 8th grade equivalent level of literacy. Subsequently, the informed consent will be signed by the volunteer making their mark in the signature section in order to document their understanding. A witness will be present to confirm the consent process has taken place. Both the witness and person conducting the consent process will sign and date the consent. The investigator obtaining consent will ask each subject to reiterate what will be required from them, risks and benefits, and their rights as a participant in order to ensure their full understanding of the study.

Non-English Speaking Subjects

Subjects who do not understand or speak English will also be eligible for this study. The consent form will be read to those non-english speaking study candidates in their primary language by a translator from the University Hospitals of Cleveland translation/International Visitors Center. A witness (who speaks English and the study subject's language) will be present to confirm the consent process has taken place. Both the witness and person conducting the consent process will sign and date the consent. The investigator obtaining consent will ask the study candidate via the translator to reiterate what will be required from him/her, risks and benefits, and his/her rights as a participant in order to ensure their full understanding of the study.

BENEFITS

There may be no direct benefit to patients from participating in this study. Their participation in the study will allow collection of valuable information about the potential benefits of zinc in persons infected with the HIV virus. This information may be useful to them and other people with HIV disease.

ALTERNATIVES

Alternatives to participation in this study are not to participate and to receive the standard of care from the patient's primary care doctor.

COST TO PARTICIPANTS

There is no cost to participants for the study related clinic visits, examinations or laboratory test required by this study. Medical costs of other treatment or examinations outside of the study will be the responsibility of the patient or their insurance company. Patients will be provided zinc supplements free of charge for the entire duration of the study. The study drug will not be provided after they finish the study (whether they complete the study or prematurely stop study participation).

PAYMENT TO SUBJECTS

For completed study visits screening, week 4 and week 10, patients will receive \$25.00 that day. Entry and week 16, patients will receive \$50.00 that day (total of \$175 for completing the entire study). This payment will help cover the expense of childcare, transportation and time off work that patients may incur as a result of being in this study. To help with the cost of gas, for participants traveling > 20-40 miles one way for their appointments, they will also be given a \$15.00 gas card to cover the cost of the

transportation. Participants traveling > 40 miles one way for their appointments will also be given a \$30.00 gas card to cover the cost of transportation. . Subjects will be asked to fast (nothing to eat or drink for 8 hours prior to visit) at entry, week 4, week 10 and week 16, therefore a \$5.00 meal voucher will be provided for subjects to use in the University Hospitals cafeteria. In addition either one all day RTA pass will be provided or a parking voucher to use in designated University Hospitals parking garages will be provided to cover the cost of transportation.

RISKS AND DISCOMFORTS: The risks for taking part in this study are:

Blood Draw: Risks associated with drawing blood include: pain, bleeding, and bruising at the site of the blood draw. Other rare risks include: lightheadedness and/or fainting or infection at the site.

EndoPat: This is a painless imaging test that has no short or long-term risks. The endoPAT test may be mildly to moderately uncomfortable because of the blood pressure cuff that is applied to the patients' arm tightly.

Fasting: Some individuals find fasting to be bothersome. It may make some individuals feel anxious, irritable, or hungry. Patients who are required to take their morning medications with food should wait until after the visit has been completed to take their medications.

Pregnancy : Zinc may not be safe for unborn babies. If patients are having sex that could lead to pregnancy, they must agree not to become pregnant or make a woman pregnant. Because of the risk involved, patients and their partner must use two methods of birth control that they discuss with the study staff. They must continue to use both methods until 6 weeks after stopping study drug. They may choose two of the birth control methods listed below:

- Birth control drugs that prevent pregnancy given by pills, shots, intra-vaginal ring or placed on or under the skin
- Male or female condoms with or without a cream or gel that kills sperm
- Diaphragm or cervical cap with a cream or gel that kills sperm
- Intrauterine device (IUD)

If women can become pregnant, they must have a pregnancy test before they enter this study. The pregnancy test must be negative. In addition, is study subjects think they may be pregnant at any time during the study, they are to tell the study staff right away. In the event that a patient becomes pregnant while on study, they will be taken off study, and no further evaluations or tests will be performed as part of the study.

Zinc Supplementation: At the doses used, uncommon side effects include nausea, vomiting, and abdominal pain (gastritis). At higher doses and when used for a long periods (years), copper deficiency

and related anemia may happen. This is extremely unlikely since we are only giving 45 mg or 90 mg daily for up to 16 weeks. Such doses have been shown to be safe even when given for 12 months to elderly frail subjects. In addition, in diseases such as Wilson's disease, zinc is given at a dose of 50 mg three times daily for prolonged durations. We will closely monitor subjects who will receive blood draws for chemistries, hematology and liver enzymes.

OTHER RISKS: Patients are informed to tell their study doctor or study nurse about all other drugs they are currently taking including non-prescription medications, alcohol, recreational, and herbal products. These drugs, if taken with the study medication, can result in dangerous interactions. If patients have questions about the drug that will be used in this study and the potential for interaction with other drugs that they take, they are instructed to ask their study doctor to provide additional information.

In addition to the risks and discomforts listed here, there may be others that are currently not known.

BIBLIOGRAPHY REFERENCED

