Zinc Supplementation and Cardiovascular Risk in HIV

NCT02856269

12/8/2016

Pilot Study of Zinc Supplementation and Cardiovascular risk in HIV

Principle Investigator:

[name], FIDSA
Professor of Pediatrics and Medicine
Director, Dahms Clinical Research Unit
Chief, Pediatric Infectious Diseases & Rheumatology

Supported by: The National Center for Complementary and Integrative Health
Grant #: 1R21AT009153

Sponsor of IND: IND Exempt

Study Team Roster:

Site Investigator: [name] | [name] | [contact] | [contact]

Research Staff: [name] | [contact] | [contact] | All CITI trained, CREC certified and IRB trained to consent study participants

[name], BSN
[name], BSN
[name]
[name]

Participating Study Site: University Hospitals Cleveland Medical Center | Site Investigator: [name] | [name] | [contact] | [contact]

Tool Revision History

Version Date: 12/08/16

Summary of Revision Made: Changes made to reflect NIH protocol template

Précis:

Study Title:

“Pilot Study of Zinc Supplementation and Cardiovascular risk in HIV infection”

STUDY OBJECTIVES

PRIMARY: To examine whether zinc significantly affect inflammation markers in HIV-infected subjects, we will assess changes overtime in inflammation markers, and correlate these changes with changes in zinc levels

SECONDARY:

- To examine whether zinc significantly affect microbial translocation in HIV-infected subjects, we will assess changes overtime in microbial translocation markers, and correlate these changes with changes in zinc levels

-To assess the safety and tolerability of 16 weeks of zinc in HIV-infected subjects

-To ascertain whether zinc significantly affect oxidative stress in HIV-infected subjects, we will assess changes overtime in oxidative markers, and correlate these changes with changes in zinc levels

- To examine the effects of zinc on systemic blood pressure, lipid and glucose metabolism in HIV-infected subjects with good virologic control, and correlate these changes with those of inflammatory and oxidative markers

STUDY ENDPOINTS

PRIMARY: The primary inflammation markers will be sCD14, sTNF-RI, and high sensitivity C reactive protein (hs-CRP).

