HOMA-IR ($r=0.58$; $p<0.0001$), sCD14 ($r=0.19$; $p=0.018$), sCD163 ($r=0.23$; $p=0.005$), hs-CRP ($r=0.30$; $p<0.0001$); IL-6 ($r=0.20$; $p=0.017$), and sTNF-RI (0.26; 0.0015). The study did not measure visceral abdominal fat or whole body measurements, but nonetheless support the hypothesis that central fat accumulation in HIV is linked to monocyte activation and systemic inflammation. The effect of zinc deficiency on body composition or metabolism is unknown.

HYPOTHESIS:

In this pilot exploratory study, our hypothesis is that short term, 16 week, zinc therapy will result in improvement in mechanisms postulated to play a role in the development and progression of HIV CVD. The endpoints are

- 1) improved serum pro-inflammatory cytokine profile
- 2) reduced oxidative stress and improved serum antioxidant status
- 3) Increased intestinal tight junctions with decreased microbial translocation

STUDY OBJECTIVES

PRIMARY: To examine whether zinc significantly affect inflammation markers in HIV-infected subjects, we will assess changes overtime in inflammation markers, and correlate these changes with changes in zinc levels

SECONDARY:

- To examine whether zinc significantly affect microbial translocation in HIV-infected subjects, we will assess changes overtime in microbial translocation markers, and correlate these changes with changes in zinc levels

-To assess the safety and tolerability of 16 weeks of zinc in HIV-infected subjects

-To ascertain whether zinc significantly affect oxidative stress in HIV-infected subjects, we will assess changes overtime in oxidative markers, and correlate these changes with changes in zinc levels

- To examine the effects of zinc on systemic blood pressure, lipid and glucose metabolism in HIV-infected subjects with good virologic control, and correlate these changes with those of inflammatory and oxidative markers

STUDY ENDPOINTS

PRIMARY: The primary inflammation markers will be sCD14, sTNF-RI, and high sensitivity C reactive protein (hs-CRP).

SECONDARY: Microbial translocation [Primarily, Lipopolysaccharide binding protein (LBP)], zinclevel, oxidative markers, safety measures (% subjects with >Grade 2 adverse events possibly or probably to study drugs), lipid levels, insulin resistance (HOMA-IR), endoPAT, and blood pressure.

INCLUSION CRITERIA:

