patients will receive two 45 mg capsules (or 90 mg). Patients will be randomized by the study pharmacist once the patient is identified and has completed screening evaluations. Patients will be given zinc gluconate capsules at a dose of 45 mg, or 90 mg, elemental zinc daily. Study drugs will be provided free of charge to study participants for the duration of their participation in the study. Antiretroviral therapy will not be provided by the study. All study visits will take place in the Special Immunology outpatient clinic. The decision for ART changes or discontinuation will be left to the primary care provider, but these changes will be documented in the study chart and will be taken into account during the analyses. Subjects will be evaluated and data will be collected according to the following schedule:

Evaluation (Weeks)	Screen	Entry*	Wk 4	Wk 10	W 16 or premature study discontinuation
Written consent form	X				
Inclusion/exclusion	X				
Family history of CVD/diabetes/HTN		X			
CVD Risk Score		X			X
Targeted physical exam/weight/blood pressure	X	X	X	X	X
Compliance assessment/safety monitoring			X	X	X
Smoking, illicit drugs and alcohol status		X			X
Dietary logs and Activity status		X			X
Height	X				
Hematology/chemistries	X	X	X	X	X
Urine β -HCG (women)	X	X	X	X	X
Fasting lipoprotein profile		X			X
Fasting insulin, glucose, HOMA-IR		X			X
Plasma inflammation markers		X			X
Microbial translocation (IFAB, LBP)		X			X
Oxidative markers		X			X
Zinc levels	X	X			X
Calcium Score		X			
DEXA		X			
Endothelial function		X			X
Resting Energy Expenditure (REE)		X			X
Stored fasting plasma, serum, urine and stool ***	X	X	X	X	X

*** Plasma, serum, urine and stool will be stored in the local laboratory in a -70 degrees freezer for potential future metabolic, cardiovascular, oxidative markers, inflammation markers, and nutrition markers. Urine will be used for possible oxidative and bone markers.

Randomization:

The randomization schedule will be performed by a statistician using SAS software to create a list based on permuted variably sized block randomization with block sizes of 4, 6 and 10 to generate 50 allocated numbers in two arms. The randomization schedule will be generated by the statisticians prior to the start of the trial by and provided to the investigational pharmacy. After being provided to the pharmacists, the randomization schedule will be maintained in a locked, secured location at the

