- Patients will fill out a dietary, physical activity, and a substance questionnaire.
- Blood will be obtained for markers of inflammation, microbial translocation, oxidative markers, glucose and insulin, chemistries, hematology, lipids and zinc. HIV-1 RNA, and CD4 count will be obtained from the clinical chart as these are part of routine care. Some of the plasma, serum urine and stool will be stored for potential future testing such as additional tests for inflammation, cardiovascular markers, endothelial function markers, oxidative markers. These

blood samples will be batched and the tests will be done at the end of the study and are part of this study.

- For woman of reproductive potential, a urine sample will be taken for a pregnancy test.
- CVD Risk Score
- Whole body DEXA scans will be done at Entry only. Limb fat, lean body mass, trunk fat, total fat, and other measurements will be measured by dual-energy absorptiometry in the anteroposterior view (using the same Hologic scanner for all subjects). An experienced technician will scan each patient using the same machine on all study subjects.
- Resting Energy Expenditure (REE) will be done at Entry and Week 16. REE will be performed in the SIU by the dietician who is experienced with this procedure using the BodyGem and MedGem Measurement Protocol. Patients will be in a fasting state for 8 hours and nicotine free for 1 hour for this test; they will be in a rested state. The total test will take about 30 minutes in a private exam room in the SIU, while the measurement takes 5-10 minutes. A single-use mouthpiece is placed into the flow tube and the device is placed on a flat surface. Subjects will be wearing a one-time use nose clip to force only mouth breathing. The subject breathes normal while the device measures the REE.
- CT scan for Calcium scoring and pericardial fat assessment will be done at Entry only. The use of cardiac CT for CAC scoring to more accurately discriminate CVD risk has grown based upon the observation that CAC occurs almost exclusively in patients with atherosclerotic vascular disease and is not present in normal coronary arteries

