- Endothelial function (EndoPAT): a non-invasive, user-independent technique using the FDA-approved EndoPAT2000 (Itamar Medical Ltd, Israel) provides a reliable and reproducible assessment of endothelial function that predicts atherosclerosis and CVD events. Using modified plethysmographic biosensors, the PAT signal is measured from the fingertip by measuring arterial pulsatile volume changes. A cuff is inflated around the upper arm to obstruct flow and released. The surge of blood flow causes endothelial dependent FMD, manifested as a reactive hyperemia. The EndoPAT® calculate the RHI, the ratio of digital pulse volume during reactive hyperemia and the baseline. In addition to the RHI, we will obtain peripheral Aix, adjusted for HR of 75, which will be compared to central Aix obtained with PWV. We have excellent track record in performing vascular studies, and carefully control for factors that could influence endoPAT; studies are performed at 24 C with the patient resting quietly. Subjects will be fasting, without smoking, caffeine, and exercise for >4 hours. Follow-up studies are completed at the same time of day as the initial study using the same equipment.

-The follow up study visits will be at 4, 10 and 16 weeks (end of study). Fasting is also mandatory for these visits. Below is the detailed events that will occur at these visits.

Week 4 and 10:

- Questionnaires about symptoms or any change in health status
- A short targeted physical exam including weight and blood pressure

- Urine pregnancy test for women
- Assess compliance/safety monitoring
- Blood will be collected for hematology/chemistries. HIV-1 RNA and CD4 count will be obtained from the clinical chart, if available.
- Plasma, serum, urine and stool will be collected and stored for potential future testing

Week 16:

- Targeted physical exam including weight and blood pressure
- Assess compliance/safety monitoring
- Questionnaire about symptoms or any change in health status, substance use and physical activity
- Dietary assessment
- Urine pregnancy test for women
- CVD Risk Score
- EndoPat
- REE
- Blood will be collected for hematology/chemistries, lipids, insulin and zinc
- Plasma, serum, urine and stool will be stored for batch testing (similar to baseline visit) to check for inflammation markers, oxidative markers, and microbial translocation. HIV-1 RNA and CD4 count will be obtained from the clinical chart.

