We hypothesize that the distribution of at least two of the four biomarkers of primary interest (hs-CRP, sCD14, sTNF-RI and LBP) will be shifted towards left after oral supplementation compared to the baseline distribution of the biomarker, see the Figure below. This shift/change in the distribution is primarily due to the location change of a biomarker. Since the random or nuisance variations are same (although nominal) in both distributions, we will perform hypothesis tests for the systematic change in the distributions due to the treatment. We will perform Kolmogorov–Smirnov (K-S) test for the differences in distributions and median test for location change. These tests will determine significant effects of zinc supplementation on the targeted biomarkers. The K-S and median tests are global test for overall significance. We will also look at the effect of zinc supplementation on individual level.

To elicit treatment effects on each individual, we will subtract baseline value of a biomarker from the post zinc supplementation measured value of the biomarker (post minus pre). The baseline subtracted values of biomarker will have either zero (no change), positive or negative values. The baseline corrected biomarker values are in continuous nature, basically the subtracted values on the real line. For measuring significance of treatment by controlling random errors, we will perform linear regression on the baseline corrected biomarker values. This analysis has similarity with the Microarray normalization method using iterative linear regression¹². The significant regression coefficient (intercept only) would indicate that the difference is due to the zinc supplement.

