Effect size consideration: As above, we previously stated that we will perform significance tests for the shift of distributions of biomarkers after the zinc supplementation using Kolmogorov-Smirnov (K-S) test. The amount of shift or effect size will be measured using Cohen's d value. For estimating the effect size, we used our statin study data as the preliminary data (NCT01218802). In the statin study the baseline mean (SD) of hs-CRP, log(sCD14), log(sTNF-RI), and LBP are 4.95(10.45), 7.71 (0.35), 7.46 (0.37), and 21.11(10.91), respectively. For each level of zinc supplementation (i.e. 45 mg or 90 mg zinc) we will compute the change in a biomarker by taking the difference of a biomarker measured before- and after- the zinc supplementation. For example, we will compute the difference in LBP measured at baseline and after the zinc supplementation. Similarly, differences will be computed for the other biomarkers. The sample size of 20 achieves 80% power to detect effect size (Cohen's $d = \text{mean difference}/\text{SD of differences}$) of 0.20 or higher using a paired t-test with a 0.10 one-sided significance level in at least two biomarker out of the four. For the combined sample size of $n=40$ (both doses combined), the estimated effect size should be higher than the threshold Cohen's $d = 0.20$. The effect size estimation is performed using nQuary Advisor 7.0 software¹⁵.

All analysis will be by intent to treat. All subjects, regardless of whether they remain on study drug, will continue to be followed throughout the duration of the study. It is standard practice in the HIV studies where inflammation markers are measured, that every attempt would be made to schedule study visits during a time that subjects are not acutely ill. That would mean that a visit would be rescheduled if a patient shows up sick, as acute illnesses may affect inflammation markers. A period of >7 days ill-free would be required. This happens rarely overall but if it does in the setting of this study, participants would be asked to come back after illness resolves.

HUMAN SUBJECTS

Institutional Review Board (IRB) Review and Informed Consent

This protocol and the informed consent document and any subsequent modifications will be reviewed and approved by the University Hospitals Cleveland Medical Center CWRU IRB. A signed informed consent form will be obtained from each study subject. The informed consent form will describe the

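### Minor: the zinc–marker association is stated on raw changes; adjusting it for the Entry marker value already collected would remove noise and part of the exposure to regression to the mean

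*Combined protocol and SAP*

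**What the plan says.** The primary objective (Précis and STUDY OBJECTIVES) has two halves, marker change over 16 weeks and its correlation with zinc change: "we will assess changes overtime in inflammation markers, and correlate these changes with changes in zinc levels". The secondary objectives on microbial translocation and oxidative stress use the same construction.

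STATISTICAL CONSIDERATIONS defines change as a simple difference: "we will subtract baseline value of a biomarker from the post zinc supplementation measured value of the biomarker (post minus pre". The one linear regression it describes has no covariate: "The significant regression coefficient (intercept only) would indicate that the difference is due to the zinc supplement". It does not return to the zinc correlation, so no coefficient, model, alpha, sample size or power is attached to it.

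The data for an adjusted model are collected. At Entry, "Blood will be obtained for markers of inflammation, microbial translocation, oxidative markers, glucose and insulin, chemistries, hematology, lipids and zinc". At Week 16 zinc is measured again, and samples are stored for batch testing, "similar to baseline visit) to check for inflammation markers, oxidative markers, and microbial translocation" (DETAILED STUDY PROCEDURES BY VISITS). The only adjustment mentioned anywhere concerns changes of antiretroviral therapy: "these changes will be documented in the study chart and will be taken into account during the analyses" (STUDY DESIGN). No method is given for it.

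**The concern.** Both arms take zinc and there is no placebo group, so a mean fall in a marker could reflect time or regression to the mean. Whether markers fall most where zinc rises most is one of the few internal signs of a biological effect.

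Read plainly, the plan correlates one raw difference with another. This has two weaknesses. First, the Entry value enters only by subtraction, so its measurement and biological noise stays in the outcome. Second, a participant whose Entry sample happened to be high in marker and low in zinc will tend to show a marker fall and a zinc rise with no zinc effect at all. Eligibility requires a low zinc reading, which makes some rebound plausible, although the schedule measures zinc at Screening and again at Entry, so part of it may be over by Entry.

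**Working it through.** **Inputs.** From the documents: combined n=40 and one-sided 0.10, both borrowed from the paired t-test calculation because the plan assigns neither to the correlation. Assumed, because the documents give no value: rho (shown from 0.3 to 0.9) and r (shown at 0.20 and 0.30, as magnitudes).

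**The plan's own figure.** No power is stated for the association. The only power statement, "The sample size of 20 achieves 80% power to detect effect size" of 0.20, concerns the mean change. It does not reproduce: a paired t-test with n=20, d=0.20 and one-sided 0.10 has 34% power per marker, and 42% for at least two of four independent markers. That is a separate and larger problem.

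**Step 1: noise.** With marker variance s² at both visits:
- Variance of the raw change: 2(1−rho)s²
- Variance of Week 16 given Entry: (1−rho²)s²
- Ratio: (1+rho)/2. At rho=0.5 this is 0.75, a 25% reduction.

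**Step 2: power.** If zinc change is unrelated to the Entry marker, the partial correlation is r/√((1+rho)/2). Fisher-z power is Φ(atanh(r)·√(n−3−k) − 1.2816), with k=0 raw and k=1 adjusted. Raw, r=0.30: atanh(0.30)·√37 = 1.883, power 72.6%. Raw, r=0.20: 48.1%.

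| rho | Partial r (r=0.30) | Power | Gain | Power (r=0.20) | Gain |
|---|---|---|---|---|---|
| 0.3 | 0.372 | 85.6% | +13.0 | 59.4% | +11.4 |
| 0.5 | 0.346 | 81.2% | +8.6 | 55.2% | +7.1 |
| 0.7 | 0.325 | 77.2% | +4.6 | 51.6% | +3.6 |
| 0.8 | 0.316 | 75.3% | +2.7 | 50.1% | +2.0 |
| 0.9 | 0.308 | 73.5% | +0.9 | 48.7% | +0.6 |

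**Step 3: spurious association.** Assume no zinc effect, unit variances, stability 0.5 for marker and zinc, n=40, nominal error 10%. The correlation of −0.3 used below is an assumption.
- Entry levels correlated −0.3, with independent movement afterwards: change–change correlation (1−0.5)²×(−0.3) = −0.075, so raw error is about 20%. Given the Entry marker, the Week 16 residual is independent of zinc change, so adjusted error is 10%.
- Transient Entry fluctuations correlated −0.3 around stable levels: correlation −0.3×0.5 = −0.15, raw error 36%. Adjusted covariance is 0 − 0.5×0.15 = −0.075; partial r = −0.075/√(0.75×0.9775) = −0.088, error 23%.
- The same, with Week 16 fluctuations also correlated −0.3: raw correlation −0.30, error 73%. Adjusted: −0.225/√(0.75×0.9775) = −0.263, error 63%.

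Simulation agrees with these to within about a point.

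**Step 4: more covariates.** Entry zinc and dose take variation out of the predictor. With stability 0.5 for both and r=0.30, conditioning on Entry zinc cuts zinc-change variance from 1 to 0.75. The marker residual after Entry marker and zinc change is 0.75−0.09 = 0.66. Partial r = 0.30√0.75/√(0.09×0.75+0.66) = 0.305. With three covariates, power is Φ(0.3146×√34 − 1.2816) = 71%, below the raw 73%. If dose takes a further 20% of that zinc variance (0.75 to 0.60), partial r is 0.275 and power 64%. In 24 simulated settings (r=0.20 and 0.30) the three-covariate model lost power in 22, and its best gain was about 2 points.

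**Step 5: the mean-change test.** Adding a sample-centred Entry value leaves the intercept equal to the mean change but shrinks its standard error by √((1+rho)/2), ignoring sampling error in the Entry mean. One-sided error becomes Φ(−1.2816×√((1+rho)/2)): 13.4% at rho=0.5 and 11.9% at 0.7, against 10%.

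**The case against.** The strongest reply is that the objective's wording is not an analysis specification. The statistical section says nothing about this correlation, so a partial correlation is not excluded. That stands: a reader might infer that the authors considered adjustment and rejected it, and the documents do not show that. Raw change against raw change is only the plain reading of the text.

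Second, no input to the power gain comes from the documents. The gain runs from about 1 to 13 points over the range of rho shown, and the one-sided 0.10 and n=40 belong to another test. This also stands, so no single figure can be called the plan's loss of power.

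Third, the precision argument assumes zinc change is unrelated to the Entry marker, while the bias argument needs them related. The two should not be added together. They are separate reasons for the same model under different conditions.

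Fourth, a reader might infer that fuller adjustment is better. Step 4 shows otherwise: the gain belongs to the Entry marker alone. Dose is also the randomised source of variation in zinc, and conditioning on it discards signal that this association is meant to use.

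Finally, this is an exploratory pilot whose powered analysis is the mean change. That limits severity, but it is no reason to leave a stated half of the primary objective on the less efficient form.

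**Conclusion.** The point holds as a minor one. As worded, the association uses the Entry marker only by subtraction, and adjusting for it is a better method at no data cost. The variance result needs only equal variances at the two visits and a linear relation. The power gain of about 5 to 9 points applies to r=0.30 with rho between 0.5 and 0.7, and becomes negligible for very stable markers.

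Two stronger readings are not supported. One is that adjustment would make a zinc–marker association trustworthy as evidence of effect. It removes Entry-driven association fully only in the simplest case of Step 3, partly in the second, and hardly at all when marker and zinc also fluctuate together at Week 16. The other is that the planned mean-change regression should be adjusted in the same way. It should not, because its error rate would rise above nominal.

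**What to change.** Add to STATISTICAL CONSIDERATIONS, for each primary inflammation marker, LBP and the oxidative markers:
- Main association model: Week 16 marker value on zinc change (Week 16 minus Entry), adjusted for the Entry marker value only, on the scale used for that marker's change. Report the zinc-change slope and partial correlation with a confidence interval whose level is stated in advance.
- Supportive: the raw change–change correlation.
- Sensitivity only: models adding Entry zinc and randomised dose, with a note that these covariates absorb zinc-change variation and usually lower power below the raw correlation.
- State the alpha and analysis n for this association. If power is claimed, give the assumed rho and r.
- State that adjustment does not remove association produced by shared fluctuation at Week 16.
- Leave the intercept-only test of mean change without an Entry covariate.

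The cost is a few sentences of SAP text and one degree of freedom per main model. No new samples, visits or measurements are needed. The slope is then read as conditional on the Entry marker.
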